2.5 Treatment Group Assignments or Randomization

Before the start of the study, computer-generated randomization schedules will be prepared. Randomization will be performed using an interactive voice or web response system. Subjects will be randomized in a 1:1 ratio to receive either CR845 0.5 mcg/kg IV or matching placebo IV during the Double-blind Treatment Period. Subjects will be stratified according to use and no use of concomitant medications to treat itching during

the week prior to randomization (Run-in Period), as well as the presence or absence of specific medical conditions, for a total of 4 strata.

All eligible subjects providing consent for participation in the Open-label Treatment Period will receive CR845 at a dose of 0.5 mcg/kg starting on Day 1 of the Open-label Treatment Period.

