2.6 Sample Size Determination

The planned sample size for this study is 350 (175 per treatment group) male and female hemodialysis subjects with chronic moderate-to-severe pruritus (mean baseline 24-hour Worst Itching Intensity NRS score >4), randomized at approximately 80 clinical sites. The sample size may be increased to 500 subjects (250 per treatment group) based on the results of a planned unblinded interim assessment conducted when approximately 50% of the planned 350 first subjects have been randomized and have either completed the 12-week Double-blind Treatment Period or have discontinued from treatment early. The planned interim assessment will be conducted by an Independent Data Monitoring Committee (IDMC). Details related to the sample size re-estimation are included in Section [11](#).

The sample size calculation is based on results of a completed phase 2 double-blind, placebo-controlled study (CR845-CLIN2101) of CR845 in hemodialysis subjects with ESRD who had moderate-to-severe pruritus. In this study, 30% of subjects randomized to the placebo group reported ≥ 3 -point improvement from baseline with respect to the 24-hour Worst Itching Intensity NRS at the end of treatment (Week 8). The proportion of subjects who received CR845 and reported a similar improvement in itch scores ranged from approximately 60% to 45% (i.e., 30% to 15% difference from placebo), depending on the dose of active study drug (0.5 mcg/kg, 1.0 mcg/kg, 1.5 mcg/kg).

Given a sample size of 350 subjects (175 per treatment group) and assuming a true response rate of 30% for the placebo group and a true response rate of 50% for the CR845 group (defining response as an improvement from baseline ≥ 3 points with respect to the Worst Itching Intensity NRS at Week 12), a 2-sided continuity corrected Chi-square will have 96% power to detect a treatment difference. The power of this test statistic would be $\geq 84\%$ for differences from placebo as low as 0.16 ([Table 1](#)).

Table 1 Power as a Function of Odds Ratio (N = 175 per arm)

Placebo Response	0.30	0.30	0.30	0.30
CR845 Response	0.50	0.48	0.46	0.45
Odds Ratio	2.333	2.154	1.988	1.909
Power^a	96%	92%	84%	79%

a. Power for a 2-sided Chi-square continuity-corrected test and a 5% Type 1 error.

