Based on results of a planned interim assessment, the sample size may be increased up to 500 subjects (250 per treatment group). Given this maximum sample size, and assuming a true response rate of 30% in the placebo group, a 2-sided continuity corrected

Chi-square would have approximately 90% power to detect a treatment difference when the CR845 response rate is 45% (a 15% difference from placebo) (Table 2).

Table 2 Sample Size as a Function of Odds Ratio (90% Power)

Placebo Response	0.30	0.30	0.30	0.30	0.30
CR845 Response	0.50	0.48	0.46	0.45	0.44
Odds Ratio	2.333	2.154	1.988	1.909	1.833
Sample Size^a	134	164	204	230	262

a. Sample size for a 2-sided Chi-square continuity-corrected test and a 5% Type 1 error.

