8.1.3 Multiplicity Handling

The efficacy of CR845 0.5 mcg/kg compared to placebo in pivotal phase 3 study CLIN3102 will be evaluated based on 1 primary and 3 secondary efficacy endpoints.

Testing of the primary efficacy endpoint will be 2-sided and conducted at the 5% error level. The study will be considered positive if the null hypothesis of no treatment difference in the primary efficacy analysis of the primary endpoint (proportion of subjects achieving ≥ 3 -point improvement from baseline with respect to the Worst Itching Intensity NRS at Week 12 of the Double-blind Treatment Period) is rejected in favor of the alternative that subjects randomized to CR845 experience significantly less itching compared to subjects randomized to placebo.

To protect the Type 1 error, a gate-keeping strategy will be implemented. Although the p-values corresponding to the hypothesis testing of the secondary variables will be reported, they will only be considered inferential if the primary analysis is statistically significant. Testing of the 3 secondary efficacy endpoints will be performed sequentially at a 2-sided 5% error level. The difference between CR845 0.5 mcg/kg and placebo with respect to the 5-D Itch total score will be tested first using the ANCOVA approach in section [8.2.4.3](#). If results are statistically significant in favor of CR845, testing with respect to the Skindex-10 total score will be conducted, also using ANCOVA. The proportion of subjects achieving ≥ 4 -point improvement from baseline with respect to the weekly mean of the daily 24-hour Worst Itching Intensity NRS at Week 12 of the

Double-blind Treatment Period will be tested only if the results of Skindex-10 total score are statistically significant in favor of CR845.

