The final p-value will be calculated using the Cui, Hung, Wang (CHW) procedure where the z-score is a weighted average of the z-score at the interim and the z-score observed for data collected after the interim, following the formula below:

$$Z_{CHW} = Z_{interim} * \sqrt{(n/N)} + Z_{post-interim} * \sqrt{(1 - n/N)}$$

where n is the number of randomized subjects at the interim and N is the initial number of subjects planned (350).

The adjusted odds ratio estimate prior to exponentiating and the 95% CI will be obtained using methodology suggested by Hung and Lawrence:

$$\hat{\delta} = \frac{r_1 \hat{\delta}^{(1)} + \sqrt{1 - r_1} \sqrt{N^* - r_1} \hat{\delta}^{(2)}}{r_1 + \sqrt{1 - r_1} \sqrt{N^* - r_1}}$$

where

$r_1 = n/350$

$N^* = (\text{Re-estimated total sample size})/350$

$\hat{\delta}^{(1)}$ = Least square mean difference from stage 1 analysis

$\hat{\delta}^{(2)}$ = Least square mean difference from stage 2 analysis

$$95\% \text{ CI} = \hat{\delta} \pm \left(\frac{\hat{\delta}}{Z_{CHW}} * 1.96 \right)$$

Note that it is possible for Z_{CHW} and δ to have opposite directions, particularly when close to zero, in which case the absolute value of the ratio will be used in the above formula.

See Section [11](#) for further details on the interim analysis.

The primary analysis and each sensitivity analysis will also be performed using the full combined dataset with the missing data imputed separately for interim subjects and post-interim subjects. No CHW adjustment will be conducted. Presentation of results will start with these analyses (additionally including the CHW results) and then follow with the results of the analysis from each individual stage.

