11. INTERIM ANALYSES AND DATA MONITORING

11.1 Sample Size Re-estimation

An unblinded interim analysis for sample size re-estimation will be conducted when approximately 50% of the first 350 subjects have been randomized and have either completed the 12-week treatment period or have discontinued from treatment early. The planned interim assessment will be conducted by an IDMC. An unblinded statistician who will not be part of the study team will provide results of the interim analysis to the IDMC members. Members of the IDMC will not participate in the Data Safety Monitoring Board (DSMB) and will not be members of the study team. During the interim assessment, the study team will remain blinded to the data; however, the IDMC will receive unblinded summary results to implement the decision rule for sample size re-estimation. The IDMC will only communicate the decision either to keep the original sample size or to increase it; no other results will be provided to blinded staff. The DSMB will be made aware of the decision, but not given the results that were the basis of the decision.

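### The 95% confidence interval for the CHW-adjusted odds ratio is unstable near zero, and too narrow if n counts subjects randomized but not yet analyzed at the interim

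*SAP*

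**What the plan says.** Under the sample size adjustment in SAP 8.2.2, imputation and logistic regression are run separately for the subjects behind the interim result and for those after it. The two z-scores are combined with weights sqrt(n/N) and sqrt(1 − n/N), "where n is the number of randomized subjects at the interim and N is the initial number of subjects planned (350").

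The log odds ratio is a weighted mean of the two stage estimates. The weights are r1 and sqrt(1 − r1)·sqrt(N* − r1), with r1 = n/350 and N* = final sample size/350. The 95% interval is the estimate ± 1.96 × (estimate / Z_CHW). Where estimate and Z_CHW differ in sign, "particularly when close to zero, in which case the absolute value of the ratio will be used in the above formula".

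SAP 11.1 places the interim at the point where about half of the first 350 subjects have been randomized and "have either completed the 12-week treatment period or have discontinued from treatment early". SAP 8.2.4.3 carries the same method over to the ≥4-point key secondary endpoint.

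**The concern.** A ratio of two random quantities that both pass through zero is a fragile standard error. The estimate uses sample-size weights, while Z_CHW uses each stage's own estimated standard error, so the two need not reach zero together. When they do not, the interval width can collapse or explode.

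The definition of n is a separate problem. Unless accrual stops, subjects randomized in the 12 weeks before the interim have been randomized but have not reached the Week 12 endpoint. Counted literally, they enter r1 without adding information to stage 1, and the condition that makes the ratio a standard error fails.

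At stake is the credibility of the adjusted interval for the primary odds ratio and for the ≥4-point endpoint.

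**Working it through.** **Inputs.** Two-sided 5% (SAP 8.1.3: "Testing of the primary efficacy endpoint will be 2-sided and conducted at the 5% error level"). 1:1 allocation (SAP 2.5). Response rates from SAP 2.6: "assuming a true response rate of 30% for the placebo group and a true response rate of 50% for the CR845 group". Planned N = 350 and maximum 500 (SAP 2.6), so N* = 1 or 500/350 = 1.429. Stage 1 has about 175 subjects (SAP 11.1).

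**1. The plan's own figure.** The plan states no coverage, so only the planning scenario can be reproduced. With 175 per arm, 30% v 50% and a continuity-corrected chi-square: (0.200 − 1/175 − 1.96·sqrt(2·0.4·0.6/175)) / sqrt((0.21 + 0.25)/175) = 0.0916/0.0513 = 1.787, a power of 96.3%. SAP 2.6 says the "Chi-square will have 96% power to detect a treatment difference". The scenario reproduces.

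**2. When the ratio is the standard error.** Put SE1 = c/sqrt(r1) and SE2 = c/sqrt(N* − r1). Then Z_CHW = [r1·d1 + sqrt(1 − r1)·sqrt(N* − r1)·d2]/c, and estimate/Z_CHW = c/[r1 + sqrt(1 − r1)·sqrt(N* − r1)]. This is exactly the standard error of the weighted estimate. The rule is therefore correct under proportional information, and only there.

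**3. At the null.** |estimate| ≤ 1.96·|estimate/Z_CHW| holds exactly when |Z_CHW| ≤ 1.96. The interval always agrees with the test, and coverage of a true null is nominal. The width is a different matter. Take r1 = 0.5, N = 500, d1 = 0.40 (SE 0.33), d2 = −0.293 (SE 0.235):
- Weights: 0.5 and sqrt(0.5)·sqrt(0.929) = 0.681, or 0.423 and 0.577 after scaling.
- Estimate = 0.423·0.40 − 0.577·0.293 = 0.0003.
- Z_CHW = 0.707·(0.40/0.33 − 0.293/0.235) = −0.0245.
- SAP standard error = 0.0122, giving an odds ratio interval of about 0.98 to 1.02.
- Actual standard error = sqrt((0.423·0.33)² + (0.577·0.235)²) = 0.195, giving about 0.68 to 1.46.

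In simulation (400,000 trials per scenario, unadjusted log odds ratios, n = stage 1 sample), the implied standard error under the null is wrong by more than 20% in about 5–7% of trials. With covariate-adjusted logistic regression (8,000 trials), it is wrong by more than 50% in about 2%, and signs conflict in about 0.6%.

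**4. If n exceeds the stage 1 sample.** At a clear effect d, the estimate is close to d and Z_CHW is close to d·k, with k = sqrt(r1)/SE1 + sqrt(1 − r1)/SE2. The SAP standard error is then close to 1/k. For N = 350 the two stages have 175 each, so SE1 = SE2 = s. With n = 286, r1 = 0.817:
- 1/k = s/(0.904 + 0.428) = 0.751s.
- True standard error = s·sqrt(0.817² + 0.183²) = 0.837s.
- Ratio = 0.897, so the standard error is 10.3% too small.

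The table repeats this for the other cases (stage 2 = 325 when N = 500), beside simulated coverage at 35–50% active response with placebo at 30%.

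| n in formula | N | Coverage | SE too small by |
|---|---|---|---|
| 175 | 350 or 500 | 94.6–95.4% | 0 |
| 240 | 350 | 90.5–93.7% | 4.5% |
| 240 | 500 | 91.9–93.6% | 4.9% |
| 286 | 350 | about 90–91.3% | 10.3% |
| 286 | 500 | about 91–92% | 9.2% |

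The values 240 and 286 are assumptions, because the documents give no accrual rate. They imply 65/12 = 5.4 and 111/12 = 9.3 subjects a week randomized and not yet through 12 weeks. In the covariate-adjusted simulation, n = 235 with 176 analyzed gives 92.4–93.4% (N = 500).

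**5. The replacement.** Estimate Z_CHW/k with standard error 1/k covers 95.1–95.3% in every case above. In the example, k = 0.707/0.33 + 0.707/0.235 = 5.15, so the standard error is 0.194 and the estimate −0.005.

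**The case against.** A reader might infer that the interval under-covers in general, or that the primary result is at risk. The documents support neither.

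- **n can be read consistently.** Protocol 8.7.1 speaks only of patients at the interim, and SAP 8.2.2 bases stage 1 on those contributing interim results. Both fit n of about 175. If stage 1 is instead everyone enrolled before the interim, as the split in SAP 8.2.3 could suggest, n matches again. When n equals the stage 1 sample, coverage is 94.6–95.4%, or 93.8–95.0% with covariate adjustment (at most about 0.7 point below an interval using the direct standard error). This stands. It also shows that the text allows readings that give different primary intervals.
- **The instability falls on trials that have not succeeded.** With n matched, the implied standard error is off by more than 20% in at most 0.02% of trials with |Z_CHW| > 1.96. The p-value, the success decision and the gatekeeping in SAP 8.1.3 use Z_CHW, not the interval. This stands.
- **Other intervals will be shown.** SAP 8.2.2 also plans an unadjusted analysis of the combined data and stage-wise results. A reader could then spot an implausible adjusted interval, but those analyses do not correct it.
- **The evidence is simplified.** The main simulation has no covariates or imputation and fixes N at 350 or 500, because the re-estimation rule is not visible. The exact coverage is therefore approximate. The algebra in steps 2 and 3 does not depend on it.

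**Conclusion.** The point holds in two limited parts. First, the interval's width is unreliable near zero whatever n means, and the absolute-value rule does not cure this. Second, under the literal definition of n with about 175 analyzed in stage 1, the interval is too narrow at non-null effects. Coverage is then roughly 90–94% across the assumed n of 240 to 286, and the standard error is about 4.5–10% too small at 50% response, which would include successful trials. With n equal to the stage 1 sample, the interval is accurate in significant trials. This is a reporting defect in the adjusted effect estimate that should be corrected. It does not threaten type I error or the trial's conclusion.

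**What to change.** In SAP 8.2.2:
- Keep Z_CHW as the test.
- Define n, and so r1 = n/350, as the subjects analyzed in stage 1. State that subjects randomized but not analyzed at the interim belong to stage 2, and align the before/after split in SAP 8.2.3.
- Report estimate = Z_CHW/k with standard error 1/k, where k = sqrt(r1)/SE1 + sqrt(1 − r1)/SE2 and SE1, SE2 come from the stage-wise MIANALYZE output. Exponentiate the estimate and its limits.
- Delete the absolute-value rule. Estimate and Z_CHW then always share a sign, and interval and test always agree.
- Apply the same to the ≥4-point key secondary endpoint.

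The cost is SAP wording and a line of code, with no new data. The drawback is that the point estimate's weights differ slightly from the cited formula. Under proportional information they coincide, because sqrt(r1)/SE1 is then proportional to r1, and sqrt(1 − r1)/SE2 to sqrt(1 − r1)·sqrt(N* − r1).

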8.2.3 Sensitivity Analyses

Sensitivity analyses of the primary efficacy endpoint will be conducted to evaluate the robustness of study results under different assumptions and imputation algorithms. For each of these sensitivity analyses, the final p-value will be calculated based on the CWH procedure, using the formula specified above.

Sensitivity 1: Early Discontinuations as nonresponders

Subjects who discontinue study drug early will be considered nonresponders (including subjects that discontinue study drug, but continue to report NRS scores as described in Section [8.1.1](#)). Subjects who do not discontinue but have missing Week 12 data will be imputed via MI as is done in the primary analysis. The imputed data will be analyzed using a logistic regression model similar to the primary analysis.

Sensitivity 2: Multiple imputation; missing not at random (MNAR)

This sensitivity analysis is an implementation of a pattern mixture model that draws from different populations based on the reason for withdrawal.

- Intermittent missing NRS scores will first be imputed using the MCMC method with the SAS MI procedure, which is appropriate for non-monotonic missing data.
- For subjects who discontinued study drug due to adverse events, NRS scores missing after discontinuation will be imputed using the distribution of the baseline value of all subjects' daily worst itching score assuming a trimmed normal (from 4 to 10).
- For subjects who discontinue due to reasons other than adverse event, missing NRS scores after subjects discontinue study drug early will be multiply imputed using multiple calls of the SAS MI procedure using data from subjects within the same treatment group who have complete data at that time, including subjects who discontinued due to adverse event. Terms will include

baseline values, the stratification values, and the weekly data through the time point being imputed. The same MI method will be used for subjects with other monotone missing data.

- The proportion of subjects who have an improvement from baseline with respect to the weekly mean of the daily 24-hour Worst Itching Intensity NRS score ≥ 3 points will be calculated for each imputed dataset
- Similar to the primary analysis, results of the logistic regression on the multiply imputed data sets will be summarized by the SAS MIANALYZE procedure.

Sensitivity 3: Tipping point analysis

Multiple imputation with mixed missing data mechanisms (MNAR for a CR845 and MAR [missing at random] for placebo) will be used to assess the robustness of the MAR assumption. This sensitivity analysis is to investigate the departure from MAR assumption by progressively decreasing the treatment differences with respect to the NRS scores over the missing visits in active treatment group until conclusion from the primary analysis is overturned. This will be applied to only Week 12 values. The MI procedure includes the following steps:

- Intermittent missing NRS scores will first be imputed using the MCMC method with the SAS MI procedure, which is appropriate for non-monotonic missing data.
- The monotone missing NRS values will then be multiply imputed with the SAS MI procedure using the monotone regression method.
- For each stage, MI will be performed within treatment group with covariates for baseline NRS score, both randomization stratification factors and the non-missing NRS scores for each week. Should convergence issues occur due to small cell size for the categorical covariates at either stage, those covariates will be removed from the model.
- For subjects in the active treatment group, a shift parameter running from 0 to 5 points in .25 point increments in PROC MI will be progressively applied to impute the missing data at Week 12, until the p-value is >0.05 .
- This sensitivity analysis will not be performed should the initial primary results fail to achieve significance

To evaluate the potential impact of the interim analysis on the properties of statistical inference at the end of the trial, the primary and sensitivity analyses of the primary endpoint will also be presented separately for the sample of subjects enrolled into the study before and after the interim analysis.

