2.3 Study Population

Subjects to be included are male and female hemodialysis subjects aged 18 years of age or older with end-stage renal disease (ESRD) who have been on hemodialysis 3 times per week for at least 3 months prior to start of screening, have moderate-to-severe pruritus (mean baseline Worst Itching Intensity NRS score >4 with at least 4 worksheets completed in the run-in period), and meet additional eligibility criteria. A full list of the inclusion and exclusion criteria can be found in the CR845 protocol (v1.0 21DEC2017).

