The baseline score will be defined as the average of the daily 24-hour Worst Itching Intensity NRS scores collected over the Run-in Period, including pre-randomization assessments collected on Day 1. As defined in the protocol, to be randomized, subjects had to report at least 4 non-missing Worst Itching Intensity scores from the start of the 7-day Run-in Period up to and including the pre-randomization assessment on Day 1. For subjects who deviated from the protocol and were randomized with more than 4 missing Worst Itching Intensity NRS scores during the 7-day Run-in Period, the baseline Itch NRS scores will be calculated using all available non-missing scores collected prior to and including the pre-randomization assessment on Day 1. These subjects will be included in the ITT population and excluded from the Per-Protocol population.

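### Sensitivity 2 imputes adverse-event dropouts without using their own baseline, so chance response depends on how severe the itch was at entry

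*SAP*

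**What the plan says.** Sensitivity 2 is a pattern-mixture analysis of the primary endpoint that treats dropouts differently by reason for withdrawal (SAP 8.2.3; the same rule for adverse-event dropouts is in Protocol 8.7.1).

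- **Adverse-event dropouts:** "NRS scores missing after discontinuation will be imputed using the distribution of the baseline value of all" trial participants. The source is described in terms of day-by-day itch ratings, and the shape is a normal cut off at 4 and at 10. The step does not mention own baseline, treatment arm or earlier scores. It gives no mean or SD.
- **Other dropouts:** multiple imputation within arm, with terms for "baseline values, the stratification values, and the weekly data through the time point being imputed". The SAP draws on subjects "who have complete data at that time, including subjects who discontinued due to adverse event".
- **Response:** the proportion with an improvement in "NRS score ≥ 3 points will be calculated for each imputed dataset". Improvement is measured from the subject's own run-in mean: "The baseline score will be defined as the average of the daily 24-hour Worst Itching Intensity NRS scores collected over the Run-in Period" (SAP 8.2.1).
- **Entry:** "mean baseline Worst Itching Intensity NRS score >4" (SAP 2.3).

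SAP 8.2.3 has two other sensitivity analyses. Sensitivity 1 counts every early discontinuation of study drug as a nonresponder. Sensitivity 3 is a tipping-point analysis that shifts active-arm imputations by up to 5 points.

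**The concern.** The draw comes from everyone's baseline, but the outcome is judged against one subject's baseline. Someone who entered at 9 and is given a typical trial-entry score may appear to have improved by 3 points. Someone who entered at 6 cannot, because no draw falls below 4. Whether an adverse-event dropout counts as a success then depends on severity at entry and a random number, and not on any stated assumption about itch after stopping.

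The plan already conditions on own baseline for the other dropouts, so the two steps of one analysis are inconsistent. At stake is how to read the only planned sensitivity analysis that separates dropouts by reason. Protocol 4.2.2 reports more adverse events on CR845 than on placebo in earlier haemodialysis studies. If adverse-event dropout follows that pattern, the extra responders fall mainly in the active arm.

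**Working it through.** **The plan's own figure.** The documents give no figure for Sensitivity 2. The design figure, used below only for scale, is 96% power at 175 per arm for 30% v 50% with a continuity-corrected chi-square (SAP 2.6). Removing the correction: n' = (√175 − 1/(0.20 × √175))² = 165.1. Then z = (0.20 × √165.1 − 1.96 × √(2 × 0.4 × 0.6)) / √(0.3 × 0.7 + 0.5 × 0.5) = 1.79, so power is 96.3%. It reproduces.

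**Inputs from the documents.** Draw trimmed to 4-10; response at 3 points or more; own baseline above 4 and at most 10.

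**Assumed, because the documents give neither.** Baseline mean 6.5, 7.0 or 7.5 and SD 1.0, 1.5 or 2.0; adverse-event dropouts have the same baseline distribution as everyone else.

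**Step 1: chance response at own baseline b.** With one draw Y, response means b − Y ≥ 3, so

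P(response | b) = P(Y ≤ b − 3) = [Φ((b − 3 − m)/s) − Φ((4 − m)/s)] / [Φ((10 − m)/s) − Φ((4 − m)/s)].

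If b ≤ 7, then b − 3 ≤ 4 and the probability is 0, whatever m and s are. Example with m = 7, s = 1.5, b = 9: (0.2525 − 0.0228) / (0.9772 − 0.0228) = 24%.

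**Step 2: the grid** (the last two columns by simulation, at least 400,000 draws per row)

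| Mean | SD | b = 8 | b = 9 | b = 10 | b ≥ 9 | All |
|---|---|---|---|---|---|---|
| 6.5 | 1.0 | 6% | 30% | 69% | 42% | 1.4% |
| 6.5 | 1.5 | 12% | 34% | 62% | 45% | 5.3% |
| 6.5 | 2.0 | 14% | 35% | 58% | 45% | 8.0% |
| 7.0 | 1.0 | 2% | 16% | 50% | 25% | 1.5% |
| 7.0 | 1.5 | 7% | 24% | 50% | 34% | 5.5% |
| 7.0 | 2.0 | 11% | 28% | 50% | 38% | 8.2% |
| 7.5 | 1.0 | 0.6% | 7% | 31% | 13% | 1.4% |
| 7.5 | 1.5 | 4% | 16% | 38% | 25% | 5.3% |
| 7.5 | 2.0 | 8% | 22% | 42% | 31% | 7.9% |

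**Step 3: the other reading of the draw unit.** If Week 12 is instead the mean of seven independent daily draws, the overall share is 0.06-2.9%. It is about 0% at b = 8, 0-11% at b = 9 and 10-90% at b = 10.

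**Step 4: effect on the comparison.** Net shift = (active minus placebo adverse-event dropout rate) × overall share. The dropout rates are assumed.

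- 10% v 5%: 0.05 × 1.4% to 0.05 × 8.2% = 0.07 to 0.41 percentage points. That is 175 × 0.10 × share = 0.2 to 1.4 extra responders on active, and 0.1 to 0.7 on placebo.
- 15% v 5%: 0.10 × 1.4% to 0.10 × 8.2% = 0.14 to 0.82 points.

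The design difference is 20 points.

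**Step 5: centring on own baseline.** With no error, improvement is 0 and chance response is 0%. With within-subject SD e (assumed) and no bounds it is Φ(−3/e): 0.13% at 1.0, 2.3% at 1.5, 6.7% at 2.0. With the draw truncated to 0-10 the overall figures are about 0.1%, 2.5% and 7-8%.

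**The case against.** Several objections stand.

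- **Intent.** A reader might infer that the rule promises no benefit after an adverse-event withdrawal and breaks that promise. Neither document states such an intent or any level of stringency. The SAP says only that different populations are used for different withdrawal reasons.
- **Direction against the primary analysis.** A reader might also infer that Sensitivity 2 flatters the active arm. Compared with the primary analysis it does the opposite. There, active adverse-event dropouts are imputed like other active subjects, about half of them responders at the 50% design rate. Here, 1-8% respond. The rule adds responders only when compared with a return to own baseline.
- **Carry-over.** The reuse of these draws for other dropouts ("including subjects who discontinued due to adverse event") might look like a second bias in the same direction. It pulls those subjects towards baseline-level itch. In one illustration (assumed 10% adverse-event and 10% other dropout on active, about 50% response), imputed response among the other dropouts fell from 49% to 43%. That is 0.10 × 6 = 0.6 points off the arm, about what the chance responders add (0.10 × 5.5% = 0.55).
- **Draw unit.** It would go too far to say that a weekly mean is drawn with daily-score spread. The text names daily scores, but it also calls them the baseline value, which is defined as an average. The trim at 4 matches the entry limit on the mean. The unit is ambiguous.
- **Other checks.** Sensitivity 1 removes the artefact for these subjects, and Sensitivity 3 adds a further check.

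None of this alters the mechanism: chance response is zero up to baseline 7 and rises with baseline above it.

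**Conclusion.** The point holds as a minor flaw in one sensitivity analysis. That baseline below 7 excludes response, while chance response rises with baseline above 7, follows from the text alone. The size rests on assumed baseline means and SDs: about 1-8% of adverse-event dropouts overall, 13-45% at baseline 9 or more, and 0.06-2.9% overall if daily draws are averaged. The effect on the treatment difference also rests on assumed dropout rates by arm and is likely under 1 percentage point, before the carry-over, which works in the conservative direction. The documents do not support reading this as a threat to the primary result or as a material inflation of the treatment effect. It is worth correcting because the artefact follows severity at entry and the change is cheap.

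**What to change.** In SAP 8.2.3, replace the rule for adverse-event dropouts with this: the weekly mean after discontinuation is drawn from a normal centred on the subject's own run-in mean, with the within-subject SD of weekly means, bounded 0-10. State that the draw unit is the weekly mean and where the SD comes from. Placebo weekly means give it directly. The run-in holds only one weekly mean per subject, so an estimate from there must be built from the daily scores. Note the change from Protocol 8.7.1 in SAP section 12.

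The cost is one sentence and a small program change before unblinding. The downside is that a few chance responders remain (about 0.1%, 2.5% and 7-8% at within-subject SD 1.0, 1.5 and 2.0), now including some with baseline below 7. At the largest SD the total is no lower than under the present rule at its upper end. The gain is that chance response no longer depends materially on baseline severity. Setting Week 12 exactly to own baseline would be simpler, but it would only duplicate Sensitivity 1 for these subjects.
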